In general, Baseline will be defined for each subject and will be defined as the last available, valid, non-missing assessment before the start of first study drug (ND0612) administration within the current study (ND0612H-012) or before the start of first study drug administration in study ND0612H-006 (for cohort 1) Unknown, Not Done, Not Applicable and other classifications of missing data will not be considered when calculating baseline observations. However, valid categorical observations will be considered for baseline calculations. All analyses will be based on the absolute changes from Baseline (not percentage), unless stated otherwise.

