5. GENERAL ASPECTS FOR DATA ANALYSIS

5.1. General Methods

All data from all patients entered into the study will be included in patient data listings. The listings will be sorted by center, and patient number (and by visit, if applicable).

The data will be summarized using either descriptive statistics (number of non-missing observations, mean, median, SD, standard error of the mean (SEM), minimum and maximum) for continuous data or frequency counts and percentages for categorical data. For visit-specific data, the number of subjects with non-missing observations at the visit in question will be used as the denominator for percent calculations. Unknown, Not Done, Not Applicable and other classifications of missing data will not be considered.

The summaries will be broken down by treatment regimen (Regimen 1, Regimen 3) and by visit, as applicable. For demographic and other baseline characteristics and selected safety data, an overall column will be displayed in addition to the data broken down by the treatment regimen. Unscheduled or repeated assessments will not be included in summary tables but will be included in listings.

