7.5. Secondary Safety Analyses

C-SSRS: The C-SSRS is a measure of suicidal ideation and behavior. The rating scale has 4 general categories: suicidal ideation, intensity of ideation, suicidal behavior, and actual attempts. All C-SSRS data will be listed. The frequency and percentage of patients with each response for suicidal ideation, intensity of ideation, and suicidal behavior items will be summarized as appropriate by visit.

QUIP: The QUIP is an instrument used to measure the extent of impulsive and compulsive behaviors in PD patients. The QUIP has 3 sections: Section 1 assesses any impulsive control disorder (gambling, sexual, buying, and eating disorders); Section 2 assesses other compulsive behaviors (punding, hobbyism, and walkabout); and Section 3 assesses compulsive medication use. All QUIP scores (A: gambling, B: sex, C: buying, D: eating, total ICD score (A-D), E: hobbyism-punding, F: PD medication use and total QUIP score (A-F)) will be summarized with descriptive statistics by visit. In addition, the changes from baseline will be summarized.

ESS: The ESS is used to determine the level of daytime sleepiness. There are 8 situations listed for which patients rate their likelihood of dozing or sleeping (0=would never doze or sleep, 1=slight chance of dozing or sleeping, 2=moderate chance of dozing or sleeping, and 3=high chance of dozing or sleeping). The total score is the sum of 8 item scores and can range between 0 and 24. If any item score is missing, the total score will be missing. The higher total score indicates the higher level of daytime sleepiness. A score of 10 or more is considered sleepy, and a score of 18 or more is very sleepy. The ESS score will be summarized with descriptive statistics by visit. In addition,

the proportion of patients who are sleepy (score of 10 or more) or very sleepy (score of 18 or more) will be tabulated by visit and treatment group.

The influence of the pump system malfunctions on the safety of ND0612 will be evaluated by capturing data on the date and time of malfunctions, including the description of the malfunction, association to an AE and the action taken. All data collected for the pump system malfunctions will be listed. In addition, the following will be tabulated by treatment group:

- The number of pump system malfunctions and the number of subjects with at least one pump system malfunction

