7.5.2. Vital Signs

Vital sign measurements include heart rate (HR), supine and standing blood pressure (BP) (both systolic and diastolic), body temperature, and weight. Furthermore, supine minus standing blood pressure (both systolic and diastolic) will be calculated. The data will be summarized with descriptive statistics by visit and treatment group. In addition, the changes from baseline will be summarized with descriptive statistics.

Furthermore, to identify potentially clinically significant vital signs, the following criteria will be used and tabulated as a shift table by visit:

- Systolic Blood Pressure: <90 mmHg (low), 90-140 mm Hg (normal), >140 mmHg (high)
- Diastolic Blood Pressure: <90 mmHg (low), 90-100 mmHg (normal), >100 mmHg (high)
- Heart Rate: <60 beats per minute (low), 60-100 beats per minute (normal), >100 beats per minute (high).

Orthostatic hypotension will be defined as a reduction in systolic BP of 20 mmHg or more, and/or a reduction in diastolic BP of 10 mmHg or more, for the standing measurement compared to the supine measurement. The proportion of patients with orthostatic hypotension will be tabulated as a shift table by visit and treatment group.

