7.5.3. ECG

The ECGs will be assessed by the investigator and deemed “Normal”, “Abnormal, not clinically significant” and “Abnormal, clinically significant” and tabulated by visit and treatment group.

In addition, the numerical ECG data generated by the central ECG laboratory will be summarized by descriptive statistics for each parameter by visit and treatment group. Also the changes from baseline will be summarized.

The QTc intervals fulfilling the following criteria will be tabulated separately using Fridericia’s correction:

- Values >500 msec
- Values increasing >15% from baseline if baseline value is ≥ 440 msec
- Values increasing >30% from baseline if baseline value is <440 msec

- Values increasing >30 msec from baseline
- Values increasing >60 msec from baseline.

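### The planned ESS tables never link a later score to the subject's own baseline, so new-onset and resolved daytime sleepiness cannot be told apart

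*SAP*

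**What the plan says.** For ESS, SAP 7.5 plans descriptive statistics of the total score ("The ESS score will be summarized with descriptive statistics by visit") and, split by regimen group, two threshold rows: "the proportion of patients who are sleepy (score of 10 or more) or very sleepy (score of 18 or more) will be tabulated by visit". Under SAP 5.1 the descriptive statistics are "number of non-missing observations, mean, median, SD, standard error of the mean (SEM), minimum and maximum", and for percentages "the number of subjects with non-missing observations at the visit in question will be used as the denominator for percent calculations". Nothing in the ESS paragraph refers to baseline.

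Other safety measures are linked to baseline. The QUIP paragraph just before it ends "In addition, the changes from baseline will be summarized". VAS pain (SAP 7.3.2), laboratory data (7.5.1) and vital signs (7.5.2) carry equivalent sentences, and the ECG section says "Also the changes from baseline will be summarized". For orthostatic hypotension, SAP 7.5.2 goes further: "The proportion of patients with orthostatic hypotension will be tabulated as a shift table by visit and treatment group".

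The protocol names excessive daytime sleepiness among its further safety objectives (7.2), lists only the ESS total score as the measure (11.1.3.2) and leaves the analysis to the SAP (11.1.4.2). Protocol 10.1.9 treats a total of 10 or more as above normal and calling for further evaluation. It schedules the ESS on Day 1, at Week 1, at Months 1, 2, 3, 4, 6, 9 and 12, at early termination and at the first safety follow-up visit.

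**The concern.** Every subject receives ND0612 and there is no untreated arm. The regimen and cohort groups allow some comparison, but they are largely non-randomised. The most direct reference for a subject's sleepiness on treatment is therefore that subject's own score before treatment.

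For a measure with a cut-off that calls for evaluation, the natural safety question is how many people below the cut-off at entry went above it on treatment, and how many moved the other way. The planned tables give only the net result of the two flows. A stable prevalence could mean that nobody changed. It could also mean that a sizeable group became sleepy while a similar number improved. These are different safety messages, and the report's tables would look the same.

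**Working it through.** The documents state no ESS prevalence, standard deviation or expected change, so there is no planned figure to reproduce. The check asks what the planned tables can and cannot identify.

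**Inputs**
- N = 210 treated subjects (protocol 11.2). SAP 3.3 gives 120-170, so both are shown.
- Proportion scoring at least 10 at each visit: assumed, 20% to 40%.
- Complete data, so that missing scores play no part.

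**Bounds from the margins.** Let b be the number scoring at least 10 at baseline and m the number at a later visit. New cases are subjects below 10 at baseline and at or above 10 later. Given only b, m and N, the number of new cases lies between max(0, m − b) and min(m, N − b).

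| N | Baseline | Later visit | b | m | New cases compatible with the table |
|---|---|---|---|---|---|
| 210 | 20% | 20% | 42 | 42 | 0 to 42 |
| 210 | 30% | 30% | 63 | 63 | 0 to 63 |
| 210 | 40% | 40% | 84 | 84 | 0 to 84 |
| 210 | 30% | 40% | 63 | 84 | 21 to 84 |
| 170 | 30% | 30% | 51 | 51 | 0 to 51 |
| 120 | 30% | 30% | 36 | 36 | 0 to 36 |

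In the second row, 210 − 63 = 147 subjects are not sleepy at entry, so new onset among them could be anywhere from 0% to 63/147 = 42.9%. When prevalence rises, the margins do give a floor: at least 84 − 63 = 21 new cases in the fourth row.

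**Two datasets with the same planned tables.** Take 210 subjects, 63 with a baseline score of 12 and 147 with a score of 6.
- Dataset A: nobody changes.
- Dataset B: all 63 sleepy subjects fall to 6, and 63 of the other 147 rise to 12.

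The Month 12 tables agree exactly. The mean is (63 × 12 + 147 × 6)/210 = 1638/210 = 7.80 and the SD is 2.76 in both; 30% score at least 10 and none at least 18. Yet there are 0 new cases in A and 63 in B.

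**What change from baseline would add.** With complete data the mean change equals the difference between the two visit means: 7.80 − 7.80 = 0 in both datasets. The SD of the change does differ. It is 0 in A and √(126 × 36/209) = 4.66 in B, since 126 subjects move by 6 points. So a change summary would show that scores moved, but not how many subjects crossed 10. Only a cross-tabulation against baseline category counts them.

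**The case against.** **A general rule may already cover it.** Protocol 11.1 says: "All analyses will be based on the absolute changes from Baseline (not percentage), unless stated otherwise". Read broadly, that would require an ESS change. It can equally be read as only choosing absolute over percentage change. SAP 5.2 words the rule for analyses that already involve a change, and the SAP's preface lets it prevail over the protocol's statistical sections where they differ. Even on the broad reading, a change summary would not count crossings. A reader might infer that the SAP omits something the protocol requires; the text is too ambiguous for that.

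**ESS is not alone.** A reader might infer from QUIP and the other contrasts that ESS was singled out. That is only partly so. VAS pain and the laboratory criteria also have threshold proportions by visit without a shift table, and C-SSRS and physical examination findings are summarised by visit only. The lack of a change summary does set ESS apart from the other numerically scored safety measures, but a shift table is written in this SAP only for vital signs and orthostatic hypotension.

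**Little is lost.** Paired scores will be in the listings (SAP 5.1), and sleepiness reported as an adverse event is tabulated (SAP 7.3.4). Both points are fair and limit the consequence. Neither produces a summary of threshold crossings on the scale itself.

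**A shift table will not prove a drug effect.** Correct: scores cross a cut-off in both directions through ordinary variation, and there is no control for it. That is a reason to show both directions, not to omit the table.

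**Conclusion.** The point holds in a limited form. No planned ESS table ties a later score to the subject's baseline, so the tables cannot separate new-onset from resolved or persistent sleepiness, whatever the completeness of the data. That conclusion is logical and rests on no model. The sizes do rest on assumption: at an assumed 30% at both visits, 0 to 63 new cases fit among 210 subjects, or 0 to 36 and 0 to 51 at the SAP's 120 and 170. These are arithmetic limits, not predictions for this trial.

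Two stronger readings are not supported. One is that the missing change-from-baseline sentence is itself what hides new cases; adding that sentence alone would leave the count unknown. The other is that drop-out biases the ESS comparison by some stated amount, which a paired change would cure. The documents give nothing from which to size or sign such an effect, and a paired change is not always closer to the truth.

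ESS is secondary and descriptive, and no decision rule depends on it. The change is desirable rather than necessary.

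**What to change.** Add to the ESS paragraph of SAP 7.5:

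1. A shift table of baseline category (below 10, 10-17, 18 or more) against the category at each post-baseline visit and against the last on-treatment score, including early termination. Include a column for subjects with no score, so that loss by baseline category can be seen. Orthostatic hypotension in SAP 7.5.2 is the precedent. Report upward and downward crossings together.
2. Change from baseline by visit, as for QUIP, to give the spread of within-subject change.

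Use the baseline in SAP 5.2. For Cohort 1 that means the score before first dosing in ND0612H-006. The documents do not say whether that study collected the ESS, and the team should check. If it did not, label the Cohort 1 Day 1 score as an on-treatment baseline, noting separately any subjects who entered after a gap of up to a month. Cohort 1 has at most 36 subjects, the number planned for ND0612H-006.

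The cost is two SAP sentences and some programming, with no new data. Output grows with eight post-baseline treatment visits plus the last on-treatment score, across up to six groups in SAP 7.1. Restricting the shift table to the combined total and the two regimens would keep it short.

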10.1.11 Infusion Pump System Issues/Problems, and Temporary Interruptions in Study Drug Infusion

Infusion pump system issues/problems will be reported to the helpline, and will be documented on a Service Report which will be forward by the helpline to the site. Temporary discontinuations of study drug infusion of more than 3 hours will be recorded by the subject in a Pump Diary (see Appendix 17.13). Infusion pump system issues/problems, and temporary interruptions in study drug infusion will be transferred to the relevant eCRF pages by site staff. The following data should be documented in the eCRF for each infusion pump system event: date and time, description, action taken, and association with AE.

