11.1.5 Other Variables

The number of issues/problems in the pump system and number of subjects with at least one event/problem will additionally be analyzed using descriptive statistics.

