5.4. Handling Withdrawals and Missing Data

In general, there will be no imputation for missing data, unless otherwise specified

The primary objective of this study is safety. Safety data will not be subject to any imputation and will be summarized on an observed case basis. For the analysis of the AEs, the incomplete follow-up will be taken into account by summarizing the data as annualized rates in addition to the

frequency counts and percentages. The analysis of the annualized rates takes into account the actual duration of the exposure to the study treatment.

For the efficacy endpoint, the missing data will be handled as follows:

- For patients who withdraw from the study, data at the early termination visit will be excluded from the by-visit summaries but will be included in the closest visit in case this visit was missing.
- For the continuous efficacy endpoints, likelihood-based modeling approach will be used to handle incomplete data. For this purpose, Mixed Model for Repeated Measures (MMRM) will be applied, see section 8.2.1.
- For categorical efficacy endpoints, the last non missing available data will be used for incomplete data.

All withdrawals will be included in all analyses up to the time of withdrawal. Subjects who are withdrawn prematurely from study drug and/or the study will be included in all analyses regardless of the duration of treatment.

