7.4.2. Treatment Compliance

The proportion of used medication out of scheduled medication will be calculated based on the actual daily administered LD dose of ND0612 and summarized with descriptive statistics. The scheduled daily medication dose will be 720 mg LD for Regimen 1 and Regimen 3 and 537.6 mg LD for Regimen 2. The total scheduled dose will be calculated as duration of treatment (as calculated in section 7.2) multiplied by the scheduled daily dose.

In addition, the number and proportion of patients with at least one prolonged treatment interruption (over 3 hours, as recorded on the corresponding CRF page) and the total number of prolonged treatment interruptions will be tabulated.

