- The number of pump system malfunctions associated with an AE and the number of subjects with at least one pump system malfunction associated with an AE
- The distribution of the actions taken regarding the malfunctions (both as subject and event counts).

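### Pump malfunctions and interruptions over 3 hours are summarised without the exposure adjustment that the SAP applies to adverse events

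*SAP*

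**What the plan says.** **Malfunctions.** SAP 7.5 tabulates by treatment group "The number of pump system malfunctions and the number of subjects with at least one pump system malfunction". It repeats the two counts for malfunctions associated with an AE, and tabulates actions taken by subject and by event. It adds that "All data collected for the pump system malfunctions will be listed". Protocol 11.1.5 plans the same pair of summaries, "The number of issues/problems in the pump system and number of subjects with at least one event/problem", analysed descriptively.

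**Interruptions over 3 hours.** SAP 7.4.2 tabulates "the number and proportion of patients with at least one prolonged treatment interruption", and says that "the total number of prolonged treatment interruptions will be tabulated". That section does not mention regimen, but the general rule in SAP 5.1 breaks summaries down by Regimen 1 and Regimen 3.

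**Adverse events.** SAP 5.4 handles incomplete follow-up by annualised rates: "The analysis of the annualized rates takes into account the actual duration of the exposure to the study treatment". SAP 7.3.4 carries an exposure-adjusted rate through its TEAE tables, including TEAEs that lead to dose adjustment or temporary withdrawal, and plans Kaplan-Meier time to first onset for the most common TEAEs.

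**Exposure.** SAP 7.2 derives duration as last minus first treatment day plus one, and reports total person-years by regimen.

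**The concern.** A subject who leaves at Month 2 has had about a sixth of the planned time in which a pump can fail or an infusion can stop. An event total and a count of subjects with at least one event both shrink as follow-up shortens, whatever the pump does. The SAP recognises this for AEs and corrects for it, but does not extend the correction to device events, which also accumulate over time on treatment. One result is uneven: an interruption that reaches the tables through a TEAE gets an exposure-adjusted rate, while one recorded only as a prolonged interruption does not.

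The issue is practical here. SAP 7.4.1 plans to explore time to discontinuation by recruitment wave after corrective actions on retention, so uneven follow-up was anticipated. SAP 7.5 also says the malfunction data serve to judge the pump's influence on the safety of ND0612. If drop-out differs between regimens, equally reliable pumps would give different table entries, and the 12-month share of subjects affected would be understated where drop-out is higher.

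**Working it through.** The plan attaches no event rate, sample size or precision figure to malfunctions or interruptions, so there is no stated figure to reproduce. The calculation below shows how far the planned summaries move when only drop-out changes.

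**Inputs**

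- Follow-up of 12 months (SAP 1.1).
- Malfunction rate L: not in the documents. Assumed 1 per person-year, with 0.25 and 4 as a range.
- Drop-out d by 12 months: not in the documents. Assumed 10% to 50%.
- Constant event rate, constant drop-out hazard, and drop-out unrelated to malfunctions: all assumed.

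**Formulas**

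- Drop-out hazard h = -ln(1 - d)
- Mean exposure in years = d / h
- Events per 100 subjects = 100 × L × d / h
- Share with at least one event = L / (L + h) × [1 - exp(-(L + h))]
- Rate per person-year = events / person-years

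**Worked case, L = 1, d = 50%.** h = 0.693. Mean exposure = 0.5 / 0.693 = 0.721 years. Events per 100 subjects = 72.1. Share with at least one = (1 / 1.693) × (1 - exp(-1.693)) = 0.482. Rate = 72.1 / 72.1 = 1.00.

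**Results at L = 1**

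| Drop-out | Mean exposure (years) | Events per 100 subjects | At least one event | Rate per person-year |
|---|---|---|---|---|
| 10% | 0.949 | 94.9 | 60.5% | 1.00 |
| 20% | 0.896 | 89.6 | 57.7% | 1.00 |
| 30% | 0.841 | 84.1 | 54.7% | 1.00 |
| 40% | 0.783 | 78.3 | 51.6% | 1.00 |
| 50% | 0.721 | 72.1 | 48.2% | 1.00 |

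With full follow-up the share would be 1 - exp(-1) = 63.2%.

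**Other event rates.** Going from 10% to 50% drop-out lowers the share with at least one event from 21.0% to 16.2% at L = 0.25, and from 95.8% to 84.5% at L = 4. Events per 100 subjects fall by 24% at every rate, since 1 - 0.721 / 0.949 = 0.24.

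**Unequal drop-out between regimens.** With a true rate of 1 per person-year in both, and drop-out of 50% in one and 20% in the other, events per 100 subjects are 72.1 and 89.6 (ratio 0.80), and the shares are 48.2% and 57.7%. The person-year rate is 1.00 in both.

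**Infusion hours.** Regimen 1 is scheduled for 24 h/day and Regimen 3 for 16 h/day (SAP 3.4). The stated rates and hours give the stated volumes: 0.08 × 6 + 0.64 × 18 = 12.00 mL, and 0.75 × 16 = 12.00 mL. If failures accrued purely per infusion hour, the person-year rate in Regimen 1 would be 24 / 16 = 1.5 times that in Regimen 3. For example, 1.5 and 1.0 per person-year both equal 0.171 per 1,000 infusion hours: 1.5 / (24 × 365.25) × 1,000 and 1.0 / (16 × 365.25) × 1,000. If failures instead arise when sets and syringes are changed, which happens daily in both regimens (Protocol 8.1.1), the person-year rate is already the like-for-like measure. The documents do not settle which applies.

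**The case against.** The best defence is that the plan gives more than it first appears, and that the endpoint is a small one. Interruptions carry a proportion, and SAP 5.1 makes percentages the default for categorical data. All malfunction data are listed, with dates and times. SAP 7.2 prints person-years by regimen, so a crude rate is one division away. Compliance in SAP 7.4.2 divides dose used by dose scheduled over the actual duration, so delivered drug is already scaled to follow-up. The additional objective is only to collect data on the pump (Protocol 7.4, SAP 2.4), and SAP 8.1 disclaims any confirmatory comparison of regimens.

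All of that is correct, and it rules out several stronger readings.

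- *That drop-out hides device failures.* No recorded failure is lost. Shorter follow-up lowers the summaries and does not suppress records.
- *That the regimens cannot be compared.* A crude rate can be derived by hand. What is missing is a specified rate with an interval and a time-to-event summary.
- *That event totals and percentages could contradict each other.* Take assumed groups of 80 and 130, equal hourly failure rates (1.5 and 1.0 per person-year) and 35% leaving evenly over the year (mean exposure 0.825 years). Totals are 80 × 1.5 × 0.825 = 99 and 130 × 1.0 × 0.825 = 107, with 67% and 54% of subjects affected. Per subject the totals are 99 / 80 = 1.24 and 107 / 130 = 0.83, the same direction as the percentages.
- *That the SAP's word malfunctions drops records the protocol calls issues or problems.* Under Protocol 10.1.11, "Infusion pump system issues/problems will be reported to the helpline", and the eCRF then takes date and time, description, action taken and association with an AE. SAP 7.5 evaluates the same fields. The terms should be aligned, but nothing shows that a record would be excluded.

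The defence does not explain why the SAP's remedy for incomplete follow-up stops at AEs.

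**Conclusion.** The gap is real and modest. Malfunctions, AE-associated malfunctions and interruptions over 3 hours are summarised without the exposure adjustment used for AEs, so the tables mix pump performance with length of follow-up. Under the assumed range, at 1 event per person-year, 10% to 50% drop-out moves the share affected from about 60% to 48% and events per 100 subjects from about 95 to 72 with no change in the true rate. Actual bias depends on the size and imbalance of drop-out, which the documents do not give.

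Three limits apply. Recovery of the true rate assumes a constant hazard and drop-out unrelated to malfunctions. If failures cluster early, the person-year rate also depends on follow-up, which is why a time-to-first-event curve should accompany it. Cohort 2 allocation to Regimens 1 and 3 was sequential and unrandomised, and Cohort 1 contributes only to Regimen 1 (SAP 3.1, 7.1), so an adjusted comparison remains descriptive. The primary analysis is not touched.

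**What to change.** In SAP 7.5 and 7.4.2 add, by regimen, for malfunctions, AE-associated malfunctions and interruptions over 3 hours:

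1. The event rate per person-year, using the SAP 7.2 exposure, with a confidence interval that allows for repeat events in one subject.
2. A Kaplan-Meier estimate of time to first event up to Month 12, censoring at the end of treatment.

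Optionally, add a supplementary rate per scheduled infusion hour: 24 h/day for Regimen 1, 16 h/day for Regimen 3, and 14 h/day for Regimen 2 periods, because switched subjects are counted in the Regimen 1 group (SAP 3.4). Note beside it that failures may arise at the daily set change, and that scheduled hours overstate actual hours when a Regimen 3 subject removes the pump at an earlier bedtime. This denominator is not derived in SAP 7.2, which counts calendar days.

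Use one term, malfunctions or issues/problems, in both documents.

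The cost is SAP wording, a few table columns and one figure. Person-years are already planned and malfunction dates and times are already collected, so the core change needs no new malfunction data.
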